## Objectives

- The purpose of this study is to implement a five-session hands-on virtual CM program (to be held weekly or bi-weekly) among patients with diabetes and elevated body mass index receiving care UT Physicians clinics serving the Acres Homes neighborhood, and comparing their outcomes to patients in usual care from UT Physicians clinics outside of the Acres Homes service area.
- The overall goals of this project are to:
  - To implement adapted virtual CM curriculum among target population
  - To assess if program participation improves participant dietary behaviors, nutrition knowledge, and cooking skills and behaviors above standard of care.
  - To assess if program participation improves patient levels of HbA1c, Body Mass Index, Blood Pressure, HDL, LDL and Triglycerides above standard of care.
  - To assess if social determinants of health modify the association between participating in the program and any of the aforementioned outcomes.
  - To determine the feasibility and reproducibility of virtual synchronous CM classes.

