- The virtual curriculum will include five 90-minute sessions (to be held weekly or bi-weekly). Participants will also be expected to shop for groceries ahead of the sessions to participate in the program. A gift card will be provided for groceries (\$40 per class = \$200 total).
- Partnership with UT Physicians sites will allow use of Electronic Medical Record (EMR) data: patient level data for HbA1c, Body Mass Index, Blood Pressure, HDL, LDL and Triglycerides collected as part of their regular standard of care and documented within the EMR. No additional visits, screenings or time will be necessary for participation in the program. Data will be abstracted and shared by clinic site to UTHealth at: baseline (within 90 days of starting the NCCM program) and at program completion (within 90 days of NCCM program completion).
- Informed consent will be obtained electronically via REDcap prior to survey administration. Participants will review the consent documents. Participants will be allowed to contact the Study Coordinator with any questions prior to completing the consent form or the survey. Participants will be allowed to leave the project at any time.
- Participants will be asked to complete an electronic 15-minute survey via REDcap at two timepoints: pre-test survey before the first class and a post-test after the conclusion of the program. The electronic pre- and post-test surveys will collect information on 1) dietary intake, 2) cooking skills, 3) cooking-related psychosocial constructs, 4) diabetes management, and 5) demographics (age, sex, race/ethnicity, education, employment status, preferred language spoken at home, and participation in government assistance programs will be collected at baseline at the start of the program). Survey items are described in detail in the measurement resource table below.

Primary Outcome- measured at both pre-survey (baseline) and post-intervention (follow-up)		
HbA1c	Measured by the clinic at baseline and follow-up	
Secondary Outcomes- measured at both pre-survey (baseline) and post-intervention (follow-up)		
Other clinical measures	Body Mass Index (height and weight), Blood Pressure, HDL, LDL and Triglycerides measured by the clinic at baseline and follow-up	
Variable (Construct)	Number of items and sample question	Source citation

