Self-efficacy in cooking food and meal planning	5 items E.g. How sure are you that you could use basic cooking techniques (e.g. microwaving, sautéing, roasting). Response options (0-4): Not at all sure to Extremely [name]., Williams, J.E., Catalano, P.M., & Griffin, S.F. (2011). Development of psychosocial scales for evaluating the impact of a culinary nutrition education program on cooking and healthful eating. Journal of Nutrition Education and Behavior, 43, 511-516.
Diabetes management	16 items E.g. The following statements describe self-care activities related to your diabetes. Thinking about your self-care over the last 8 weeks, please specify the extent to which each statement applies to you.	Schmitt, A., Gahr, A., Hermanns, N., Kulzer, B., Huber, J., & Haak, T. (2013). The Diabetes Self-Management Questionnaire (DSMQ): development and evaluation of an instrument to assess diabetes self-care activities associated with glycaemic control. Health and quality of life outcomes, 11(1), 1-14.
Tertiary - measured at both pre-survey (baseline) and post-intervention (follow-up)		
Nutrition knowledge	1 item E.g. When thinking about preparing a plate of food, how much of your plate should be filled with fruits and vegetables?	Not previously validated, pilot tested in APHL

Covariates- baseline only		
Food Insecurity	2 items e.g., "Within the past 12 months we worried whether our food would run out before we got money to buy more?"	Hager, E.R., Quigg, A.M., Black, M.M., Coleman, S.M., Heeren, T., Rose-Jacobs, R., Cook, J.T., De Cuba, S.A.E., Casey, P.H., Chilton, M. and Cutts, D.B., 2010. Development and validity of a 2-item screen to identify families at risk for food insecurity. Pediatrics , 126(1), pp.e26-e32.
Internet Access	4 items e.g., Do you ever go on-line to access the Internet or World Wide Web, or to send and receive e-mail?	From: HINTS 5, Cycle 4 – Section B: Using the Internet to Find Information, in HINTS 5, Cycle 4 (2020) Methodology Report. https://hints.cancer.gov/docs/methodologyreports/HINTS5_Cycle4_MethodologyReport.pdf
Health Literacy	3 items e.g., How often do you have problems learning about your medical condition because of difficulty understanding written information?	Chew, L.D., Bradley, K.A., & Boyko, E.J. (2004). Brief questions to identify patients with inadequate health literacy. Family Medicine , 36(8): 588-594.

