### **Statistics**

- 132 participants are planned to be enrolled, 66 from intervention clinics and 66 from control clinics.
- All participants that enroll in the program will be included in the analysis. Saturation point is considered attendance of 4 out of 5 sessions (80%).
- Statistical analysis will include descriptive and frequency analysis of responses, a pre-post analysis using paired t-test, chi-square test, and Analysis of Covariance to determine changes in biometric and behavioral measures pre to post NCCM program participation.
- Level of significance will be set at  $p < 0.05$ .
- Qualitative data will be analyzed for themes using standard methods and NVivo software. Responses will be summarized, and a report will be created to provide information to our research investigators and the public health community.

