### **Data handling and record keeping**

- Electronic Medical Record (EMR) data: Clinic, demographic and healthcare utilization data will be stored in the UT Physicians database. UT Physicians' team members will create custom extract report from the EMR for the participating patients. The report will be sent to UTHealth CMS Certified Data Center as a HL7 using existing UT Physicians protocols. Patient level data for HbA1c, Body Mass Index, Blood Pressure, HDL, LDL and Triglycerides collected as part of their regular standard of care and documented within the EMR will be abstracted by and provided by UT Physicians to the study team at baseline (within 90 days of starting the NCCM program) and at program completion (within 6 months of NCCM program completion).

- All data will be kept confidential and stored on UTHealth Houston SPH computers on password protected share drives. All survey information will be securely collected and stored in REDCap data management software at UTHealth. Study codes in the form of a unique number will be assigned to each participant to label their response. A separate electronic password protected document that links the study code to subjects' identifying information (name, phone number, email, zip code of residence) will be stored on UTHealth Houston SPH computers on password protected share drives. Only aggregate data will be reported and published.
- Data on EMR outcomes will be linked to survey data based on a series of variables collected (name, DOB, zip code). Once the data is linked, the individual's record will be assigned a dummy ID and all direct identifiers removed for safety issues. A crosswalk that would allow for re-identification will be kept on a separate file stored in an encrypted external drive securely saved under key UTHealth Houston SPH office.
- All interviews will be recorded and transcribed. Transcriptions will be edited to exclude names and other identifying information. All audio files will be destroyed after they are transcribed and analyzed. Audio and transcription files will be stored on UTHealth's secure server, on password protected drives. Data handling procedures will be overseen by [name].

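### The chi-square test listed for pre-to-post change is not specified as paired; run as an ordinary chi-square on categorical survey items it would give invalid, usually conservative, p-values

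*Combined protocol and SAP*

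**What the plan says.** The Statistics section names the methods in one sentence: "a pre-post analysis using paired t-test, chi-square test, and Analysis of Covariance". The same sentence gives their purpose: "to determine changes in biometric and behavioral measures pre to post NCCM program participation". It does not say which variables each test is for, which kind of chi-square is meant, or whether the contrast is between time points or between arms.

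The data are paired. Under Study Procedures, "Participants will be asked to complete an electronic 15-minute survey via REDcap at two timepoints", and under Data handling and record keeping, "Study codes in the form of a unique number will be assigned to each participant to label their response". Each person's two answers can therefore be linked. No paired method for categorical data is named anywhere in the document.

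On numbers, Statistics states that "132 participants are planned to be enrolled, 66 from intervention clinics and 66 from control clinics". Significance is set at p < 0.05, with no statement of sidedness.

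One objective is to see whether the program "improves participant dietary behaviors, nutrition knowledge, and cooking skills and behaviors above standard of care". The clearest categorical item in the measurement table is the single nutrition-knowledge question, classed as tertiary: "When thinking about preparing a plate of food, how much of your plate should be filled with fruits and vegetables".

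**The concern.** The ordinary (Pearson) chi-square test assumes that the two sets of answers come from different people. Here each person contributes one answer to each set. The plan recognises this for continuous measures by writing paired t-test, but an unqualified chi-square stands next to it in the same list. An analyst who follows the sentence literally would set pre against post counts in a two-by-two table and run Pearson's test, which uses the wrong variance for a within-person change.

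Two things are at stake. If a person's two answers are positively correlated, the test is too strict, and real gains in categorical items could be missed in a pilot meant to inform a full-scale trial. Separately, any pre-post test within one arm leaves the control arm out, so it cannot address the comparison with usual care that the objective asks for.

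**Working it through.** The plan states no power, effect size, correlation or sample-size derivation, so there is no figure of its own to reproduce.

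**Inputs from the documents:** 66 participants per arm; significance level 0.05; two surveys per person.

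**Assumed:** two-sided testing; all 66 people answer both surveys; a binary item with p1 = 35% correct before and p2 = 50% after; within-person correlation phi from 0 to 0.5.

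**Step 1, size when nothing changes.** With equal margins, the true variance of the difference is (1 − phi) times the variance that the ordinary chi-square uses. The actual size of a nominal 5% test is then 2 × [1 − Φ(1.96/√(1 − phi))]:
- phi 0: 5.0%
- phi 0.3: 2 × [1 − Φ(1.96/√0.7)] = 1.9%
- phi 0.5: 2 × [1 − Φ(1.96/√0.5)] = 0.6%

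Simulation with 66 pairs at 50%/50% agrees: 4.5%, 1.7% and 0.5%, while asymptotic McNemar stays near 5%. At phi = −0.2 the error reverses slightly, to 6.6%.

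**Step 2, power by formula.**
- True variance of the difference: [p1q1 + p2q2 − 2·phi·√(p1q1p2q2)]/n, with p1q1 = 0.2275, p2q2 = 0.25 and √(0.2275 × 0.25) = 0.2385.
- Variance used by chi-square: 2 × 0.425 × 0.575/66 = 0.00740, SE 0.0861. The test needs a difference of 1.96 × 0.0861 = 0.1687 to reject.
- phi 0.3: true SE = √[(0.4775 − 0.1431)/66] = 0.0712. Chi-square power = Φ[(0.15 − 0.1687)/0.0712] = 40%. Paired test = Φ(0.15/0.0712 − 1.96) = 56%.
- phi 0.5: true SE = √[(0.4775 − 0.2385)/66] = 0.0602. Chi-square power = Φ[(0.15 − 0.1687)/0.0602] = 38%. Paired test = Φ(0.15/0.0602 − 1.96) = 70%.

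**Step 3, power by simulation (same scenario).**

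| phi | Ordinary chi-square | McNemar, asymptotic | McNemar, exact |
|---|---|---|---|
| 0 | 41% | 41% | 34% |
| 0.2 | 40% | 50% | 41% |
| 0.3 | 39% | 56% | 46% |
| 0.5 | 37% | 70% | 61% |

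Against asymptotic McNemar the loss is 0, 10, 17 and 33 points. Against exact McNemar it is about 1, 7 and 24 points at phi 0.2, 0.3 and 0.5, and at phi 0 the exact test is the weaker of the two. Correlations near 0.7 are left out: for these proportions the mathematical maximum is about 0.73, so almost nobody could move from right to wrong.

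**Step 4, the other literal reading.** A chi-square on the pre-by-post cross-table tests whether the two answers are associated, not whether they changed. With no change at all (50% at both times, 66 pairs), it rejects 69% of the time at phi 0.3 and 99% at phi 0.5.

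**Step 5, reach.** HbA1c, BMI, blood pressure and lipids are continuous. Most survey measures are ordinal items or multi-item scales. That leaves the one-item knowledge question and any other item that is analysed as categories.

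**The case against.** The strongest reply is that the sentence is a loose list for a two-arm study. It names no variable and no contrast. McNemar's test is itself a chi-square test, and Pearson's test is valid for comparing categorical variables between intervention and control. On either reading nothing is wrong except brevity. This stands in part: the text does not prove that an ordinary chi-square of pre against post is intended. But the sentence ties the listed tests to change over time and marks only the t-test as paired, so that is the more natural reading. An analyst could not tell from the plan which test to run.

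The reply also holds on reach. Only one outcome is clearly touched, a single tertiary item, and the sentence speaks of biometric and behavioral measures, which may not cover knowledge. No dichotomising of other items is planned. Against this, nutrition knowledge is named in the objectives and no other analysis is given for it.

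The power figures rest on assumed proportions, an assumed correlation and complete follow-up. They also describe a within-arm McNemar test, so they do not measure the power of a comparison between arms. Both points stand.

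**Conclusion.** The concern holds in conditional form. If the listed chi-square is run as an ordinary test of pre against post answers, its p-values are invalid whenever the within-person correlation is not zero. At phi 0.3 to 0.5 the actual size falls to about 1.9% to 0.6%. In the assumed scenario (66 complete pairs, 35% to 50%, two-sided 5%) power is 17 to 33 points below asymptotic McNemar and 7 to 24 points below exact McNemar. At phi 0 nothing is lost.

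A reader might infer more, and the documents do not support it:
- That the plan definitely assigns Pearson's test to categorical pre-post answers: the sentence names no variables and no type of chi-square.
- That much of the power is certainly lost: this depends on a correlation the documents do not give.
- That false claims of benefit would follow: at positive correlation the ordinary pre-against-post test errs in the conservative direction.
- That the trial's main result is at risk: HbA1c and the other clinical measures are continuous and unaffected.

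Whichever chi-square is meant for pre-post change, a within-arm test does not address improvement beyond usual care.

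**What to change.** In the Statistics section:

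- **Within-arm change in categorical items:** replace the chi-square test with McNemar's test (Stuart-Maxwell for more than two categories), or a paired difference in proportions with its confidence interval, presented as description.
- **Comparison with control:** use logistic regression of the post answer on arm, adjusted for the pre answer, with a proportional-odds model for ordered categories. This is the analysis that answers the objective. GEE or mixed logistic models with a group-by-time term would be a reasonable alternative.
- **Chi-square:** keep it only for comparisons between the two arms, such as baseline characteristics.
- **Assignment:** state which variables get which test, naming the nutrition-knowledge item and any other item to be analysed as categories, and state that tests are two-sided if that is intended.

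The cost is a sentence or two of text. The study codes already allow each person's two surveys to be linked, so no new data, visits or participants are needed.

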### **Ethics**

- We will obtain informed consent from all interested participants during the technology screening before the first session. The participants will be given a digital consent via REDcap to review and acknowledge, a copy of the consent will be sent to the email provided by the patient. Patients will have the opportunity to pause signing of the consent in order to ask any questions they may have.

### **Data handling and record keeping**

- Electronic Medical Record (EMR) data: Clinic, demographic and healthcare utilization data will be stored in the UT Physicians database. UT Physicians' team members will create custom extract report from the EMR for the participating patients. The report will be sent to UTHealth CMS Certified Data Center as a HL7 using existing UT Physicians protocols. Patient level data for HbA1c, Body Mass Index, Blood Pressure, HDL, LDL and Triglycerides collected as part of their regular standard of care and documented within the EMR will be abstracted by and provided by UT Physicians to the study team at baseline (within 90 days of starting the NCCM program) and at program completion (within 6 months of NCCM program completion).

- All data will be kept confidential and stored on UTHealth Houston SPH computers on password protected share drives. All survey information will be securely collected and stored in REDCap data management software at UTHealth. Study codes in the form of a unique number will be assigned to each participant to label their response. A separate electronic password protected document that links the study code to subjects' identifying information (name, phone number, email, zip code of residence) will be stored on UTHealth Houston SPH computers on password protected share drives. Only aggregate data will be reported and published.
- Data on EMR outcomes will be linked to survey data based on a series of variables collected (name, DOB, zip code). Once the data is linked, the individual's record will be assigned a dummy ID and all direct identifiers removed for safety issues. A crosswalk that would allow for re-identification will be kept on a separate file stored in an encrypted external drive securely saved under key UTHealth Houston SPH office.
- All interviews will be recorded and transcribed. Transcriptions will be edited to exclude names and other identifying information. All audio files will be destroyed after they are transcribed and analyzed. Audio and transcription files will be stored on UTHealth's secure server, on password protected drives. Data handling procedures will be overseen by [name].

### **Quality control and assurance**

- Respondents' email will be kept on a password-protected computer and can be used to correct ID's if needed.
- The surveys will be administered electronically and all participants will complete the survey prior to and after the intervention program. Any participants that do not attend the last class will be contacted by phone and email to complete the electronic post survey. Before analyses are conducted, the raw data will be reviewed for completeness.

### **Publication Plan**

- Investigators at UTHealth will submit manuscripts based on the results of the project to academic journals for publication. All manuscripts will include de-identified data.
- This culinary medicine program will be conducted in partnership with UT Physicians and have the potential to be integrated into existing programs.
- In addition, this program will provide preliminary data that can be used for a full-scale trial.

### **ATTACHMENTS**

1. Study Consent Form
2. Pre/ Post Survey

